### **ABR:**

The ABR is the main efficacy endpoint of the secondary objective.

- ABRs will be presented for all bleeds, joint bleeds, spontaneous bleeds, , and trauma bleeds
- Results for the main efficacy period (Visit 3 to end of study) will be displayed by treatment regimen as described in section [4.1](#)
- Results for the complete study period (baseline to end of study) will be shown for the combined prophylaxis group

### **Other efficacy endpoints**

Unless otherwise mentioned, results will be presented for complete study periods.

- Percentages of participants with 0 bleeds, 0 joint bleeds, 0 spontaneous bleeds, during the following treatment periods:
  - Last 6 months
  - Last year

- Treatment administration (overall, prophylaxis, treatment of bleeds): number of infusions (all and per year), consumption (IU, IU/kg, IU/kg/year, IU/kg/infusion, IU/year, IU/infusion)
- Reason for infusion
- Bleeding attributes: type, location, intensity, number of infusions to control, response to treatment
- FVIII levels pre- and post-infusion and incremental recovery: Results will be displayed by visit and overall (means per participant across visits)
- Pre- and post-infusion FVIII levels which are invalid for the calculation of recovery will be listed
- Bleeds into pre-existing target joints (annualized number, proportion of participants with 0 such bleeds) for the complete study period as well as the main efficacy period (starting with Visit 3)
- All untreated bleeds of study 19764 will be listed.
- Dosing regimens at baseline, Visit 3, and end of study will be compared in shift tables
- All dosing frequencies, planned doses, and reasons for dose modifications will be listed

[figure not shown]
### Pooled efficacy analysis:

Pooled ABRs will be presented for the combined prophylaxis group and complete study periods. Only subjects who participated in the extension periods will be included in the analysis. Participants from study 13024 who only received on-demand treatment will be excluded from the pooled efficacy analysis because on-demand treatment was not applied in the other studies and pooling of on-demand and prophylaxis participants is not meaningful for efficacy endpoints. Participants who switched from on-demand treatment in the main study to prophylaxis in the extension part of study 13024 will be included in the prophylaxis group with their prophylaxis treatment period. The on-demand main study part of these participants will not be included in the analysis. Results will be displayed by age group.

### Sensitivity analyses:

- Estimates and 95% confidence intervals from a negative binomial regression model will be presented for the ABRs of all bleeds, different lengths of evaluation periods will be addressed via an offset variable
- A subject listing including number and kind of bleeds and time in study will be provided for participants excluded from the mITT set

CCI

CCI

### **6.3 Pharmacokinetics/pharmacodynamics**

Pharmacokinetic and pharmacodynamic parameters are not evaluated in this study.

### **6.4 Safety**

All safety analyses will be performed on the SAF. MedDRA codes of studies 13024 and 15912 will be updated by the MedDRA version used for study 19764. An AE will be considered treatment-emergent if it starts after first injection and not later than 7 days after last injection of Jivi.

Overview tables displaying all AEs, all pre-treatment AEs and all treatment emergent adverse events (TEAEs) will be created. All subsequent tables will be presented by MedDRA preferred term (PT) and system organ class (SOC). Serious AEs, TEAEs, serious TEAEs, drug-related TEAEs, serious drug-related TEAEs, TEAEs of special interest, TEAEs causing discontinuation of study drug, TEAEs by maximum intensity, drug-related TEAEs by maximum intensity, non-serious TEAEs, and AEs leading to death will be presented.

Overview tables, all TEAEs, serious TEAEs, drug-related TEAEs and serious drug-related TEAEs will be displayed by subgroups.

### **Factor VIII inhibitor, PEG antibody and BAY 94-9027 antibody results**

Frequency tables will be provided for the number of participants with confirmed inhibitors and anti-drug and anti-PEG antibodies. The status during study will be displayed by pre-treatment status. Proportion of participants with positive measurements at the end of the observation period will be displayed based on the number of participants with positive status during study.

Inhibitors will be classified as being either low titer ( $\geq 0.6$  BU/mL and  $\leq 5$  BU/mL) or high titer ( $> 5$  BU) based upon persistence of an inhibitor.

Antibody incidences at screening/baseline as well as new antibody incidences after start of treatment will be presented.

## Statistical Analysis Plan

---

**BAY 94-9027 / 19764**

Page: 15 of 17

Subject listings will be provided for all participants from study 19764 with at least one positive FVIII inhibitor measurement/BAY 94-9027 antibody measurement/PEG antibody measurement/PEG IgM antibody measurement showing all FVIII inhibitor/BAY 94-9027 antibody/PEG antibody/PEG IgM antibody (respectively) laboratory measurements as well as FVIII recovery results of these participants, including the number of ED before the measurement dates and the date of the last injection before measurement dates.

All measurement results for inhibitors including repeated measurements in case of positive results will be displayed by time point and presented in subject listings.

### **Clinical laboratory**

Number of participants with treatment emergent high and low laboratory abnormalities will be displayed in frequency tables by laboratory category.

Summary statistics for all laboratory values at baseline and individual last visit will be presented. Changes from baseline at last visit will be provided, if applicable.

Shift tables for urinalysis parameters will be shown.

In addition, summary statistics for all laboratory values and changes from baseline by visit will be displayed for study 19764.

Laboratory results will not be displayed by subgroups.

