#### **9.4.2 Safety Analyses**

All safety analyses will be performed on the Safety Population. Laboratory findings, adverse events, concomitant medications, vital signs, and medical history data will be provided in subject listings.

Those participants who were given at least one dose of Jivi will be valid for the safety analysis. Inhibitor development will be summarized by time point and presented in subject listings. The purpose of the listing is to delineate the clinical factors which may be positively associated with development of the inhibitor. Confirmation of positive inhibitor titers (Bethesda  $\geq 0.6$  BU/mL) will require repeat measurement. If the repeated inhibitor result is  $<0.6$  BU without intervention, the inhibitor is not confirmed and should not be reported as an SAE. Inhibitors will be classified as being either low titer ( $\geq 0.6$  BU/mL and  $\leq 5$  BU/mL) or high titer based upon persistence of an inhibitor  $>5$  BU. Participants will also be monitored for other antibodies against the drug substance Jivi and/or PEG. Proportions of participants with inhibitor or antibodies will be presented in an overview table.

Laboratory values and vital signs will be summarized. Individual listings of AEs (including AEs as reported, start, duration, severity, relation to study drug) will be provided. The incidence of treatment-emergent adverse events (AEs) will be summarized using the Medical Dictionary for Regulatory Activities (MedDRA). An AE will be considered treatment-emergent if it starts after first injection and not later than 7 days after last injection of Jivi.

Integrated safety analyses will be done based on combined data from this study and studies 13024 Part A and 15912. Summary tables for demographics, baseline characteristics (including gene defect), medical history (including family history of hemophilia and history of inhibitor), concomitant medications, extent of exposure, treatment-emergent AEs, and laboratory findings will be provided. Results will be provided by age groups.

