## 4. General Statistical Considerations

### 4.1 General Principles

The study is not designed to test any predefined hypothesis. All analyses will be descriptive or exploratory.

The statistical evaluation will be performed by using the software package SAS release 9.2 or higher (SAS Institute Inc., Cary, NC, USA). All variables will be analyzed by descriptive statistical methods. The number of available and missing data, mean, standard deviation, minimum, quartiles, median, and maximum values will be calculated for metric data. Frequency tables will be generated for categorical data.

In addition to the analyses for study 19764, pooled results across the clinical phase 3/phase 4 studies will be presented. Therefore, data of study 19764 will be pooled with data from studies 13024 and 15912. CCR

Except when mentioned otherwise, all safety analyses will present results for study 19764 and pooled results of studies 19764, 13024 Part A (incl. Part A extension) and 15912 (incl.

extension). All safety analyses will be presented for the combined Jivi treatment group and will not distinguish between different regimens or treatment frequencies.

Efficacy analyses will be done for study 19764. If presented by treatment regimen, this will refer to the regimen at Visit 3. Participants who switch their regimen after Visit 3 will be assigned to a 'Variable frequency' group. Participants who dropped out before Visit 3 will be analyzed with their baseline regimen.

In addition to the study specific efficacy analysis, pooled results from studies 19764, 13024 Part A (incl. extension), and 15912 (incl. extension) for the main efficacy endpoint, i.e. annualized bleeding rates (ABR), will be provided.

Data handling rules described in this SAP refer specifically to study 19764. Data handling will be consistent with the data handling already applied to studies 13024 Part A and 15912. More details about the data handling of studies 13024 Part A and 15912 are available in the SAPs of these studies.

The following subgroup will be analyzed for safety and pooled efficacy:

- Age group 1: <12 years vs  $\geq$  12 years (at enrollment)

Subgroup tables will not be displayed by study/pool but by subgroup categories instead.

In case of multiple measurements before first treatment, the last one will be analyzed as baseline measurement.

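### SAP 6.4 drops the age-group display of pooled laboratory results that Protocol 9.4.2 promises, and SAP section 7 does not record the departure

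*SAP*

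**What the plan says.** Protocol 9.4.2 describes integrated safety analyses of study 19764 with studies 13024 Part A and 15912. Its list of summary tables ends with "treatment-emergent AEs, and laboratory findings will be provided. Results will be provided by age groups".

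SAP 4.1 names one subgroup, age at enrolment <12 vs ≥12 years, under the words "The following subgroup will be analyzed for safety and pooled efficacy". It also sets the scope of the safety output: "Except when mentioned otherwise, all safety analyses will present results for study 19764 and pooled results of studies 19764, 13024 Part A" and 15912, with the extensions.

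SAP 6.4 then treats the types of safety output differently:

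- Adverse events keep the split: "Overview tables, all TEAEs, serious TEAEs, drug-related TEAEs and serious drug-related TEAEs will be displayed by subgroups".
- Laboratory data lose it: "Laboratory results will not be displayed by subgroups".
- The laboratory output consists of counts of treatment-emergent high and low abnormalities, changes from baseline at last visit where applicable, urinalysis shift tables, and this: "Summary statistics for all laboratory values at baseline and individual last visit will be presented". By-visit laboratory summaries are planned for study 19764 only.

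SAP section 7 notes that version 2 cut the subgroups to the single age split and removed the by-study safety columns for 13024 and 15912. It does not mention taking the age split away from laboratory data.

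**The concern.** A protocol commitment on safety reporting is not carried into the SAP, and a reader of the SAP's change record would not learn this. The record says that results are stratified by age.

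The omission matters more because the by-study columns have also gone. Without them, the age split was the remaining way for this report to show children's laboratory summaries separately from those of older participants. As written, each pooled laboratory table merges PROTECT Kids with PROTECT VIII and the adult phase IV study. Protocol 2.2 gives the development programme an age range of 2 to 65 years. Laboratory values in growing children may change between baseline and last visit for reasons unrelated to treatment, and a merged mean change or abnormality count cannot show which age group it came from.

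Protocol Table 10-1 gives renal safety under long-term PEG exposure as the purpose of the urine samples and their biomarkers. The urinalysis shift tables are among the outputs that lose the age display.

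**Working it through.** **Inputs.** All counts are from the table in Protocol 9.2: PROTECT VIII 134, PROTECT Kids 73, planned phase IV study at least 25, expected total at least 232. Protocol 5.1 sets a minimum age of 18 for study 19764. The documents give no size for age-related laboratory change.

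**Step 1: reproduce the plan's total.** 134 + 73 + 25 = 232, which matches.

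**Step 2: shares of the pool.**
- PROTECT Kids: w = 73/232 = 0.315.
- The other two studies: (134 + 25)/232 = 159/232 = 0.685.
- With 30 enrolled in study 19764, the upper end of the planned range: w = 73/237 = 0.308.

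**Step 3: what the pooled mean change shows.** Let c be the mean change in PROTECT Kids and r the mean change in the rest. Then

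pooled mean change = w·c + (1 − w)·r = 0.315c + 0.685r.

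- *Mimic.* If r = 0, the pooled change is 0.315c. A change confined to the children's study appears at 31.5% of its size, a dilution of 1/0.315 = 3.2-fold, and nothing in the table shows that it comes from children alone.
- *Mask.* The pooled change is zero when r = −(w/(1 − w))·c = −(73/159)·c = −0.46c. A change in the 159 others that is 46% as large as an opposite change in the children would vanish from the pooled mean.

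These are proportions only. Turning them into laboratory units would need values of c and r, which the documents do not give.

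**Step 4: abnormality counts.** The same weights apply. As an illustration with assumed rates, 10% in PROTECT Kids and 2% in the rest pool to 0.315 × 10% + 0.685 × 2% = 4.5%. With the rates reversed, they pool to 7.5%. In neither case does the pooled rate describe either group.

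**Step 5: which tables are affected.** Study 19764's own laboratory tables, including those by visit, contain adults only and are not mixed. The pooled abnormality, baseline, last-visit, change and urinalysis shift tables are.

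**The case against.** **The protocol section is only a summary, and the SAP may be more specific.** Protocol 9.4 does describe its text as a summary, and the sentence in SAP 6.4 reads as a deliberate exception to the general rule in 4.1. A reader might infer that the SAP contradicts itself. That reading is weak, because a specific exception can stand beside a general rule. What stands is the conflict with Protocol 9.4.2 and the lack of any record of it in SAP section 7.

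**Children's results are already available.** SAP section 7 drops the by-study display for 13024 and 15912 because it would repeat existing results. If PROTECT Kids is essentially the <12 group, a <12 column would largely repeat study 15912. This is a fair argument for low urgency. However, the stated reason concerns the by-study display and says nothing about laboratory data by age, and the protocol promised the age display in the integrated analysis itself.

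**Other outputs limit the damage.** Protocol 9.4.2 also provides laboratory findings in subject listings, the main adverse-event tables keep the age split, the primary endpoint is inhibitor development, and every analysis is descriptive. All of this is correct and keeps the point moderate. Listings still do not replace promised summaries.

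**A renal signal would be hidden.** A reader might infer this, and the documents do not support it. Table 10-1 ties renal safety under PEG exposure to the urine samples and gives no such purpose for the chemistry panel. Nothing says that the urine biomarkers were measured in 13024 or 15912. Nor do the documents say how long participants stayed in the extensions, how any analyte moves with growth, or whether high and low flags use age-specific limits.

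**A baseline gap between children and adults inflates the spread.** This would affect the spread of pooled levels. A fixed gap cancels in each participant's change from baseline, so it does not show that a change would be missed.

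**Conclusion.** The point holds as a departure from Protocol 9.4.2 that the SAP does not declare, confined to the pooled laboratory tables. The textual conflict is certain. Its consequence is a possibility: a change confined to PROTECT Kids appears at about 31.5% of its size in the pooled mean change (30.8% if 30 are enrolled), and age-related change in children could mask or mimic a laboratory signal to an extent that cannot be quantified from the documents.

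This rests on three assumptions. First, PROTECT Kids is taken as the <12 group; its name and the events reported in children under 6 years suggest this, but its age range is not stated. Second, 73 and 232 count participants included, and the numbers with both baseline and last-visit values may differ. Third, the analytes concerned were measured in the earlier studies as well as in study 19764.

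The inhibitor endpoint and study 19764's own laboratory results are untouched. The change should be made, but it does not threaten the study's main conclusion.

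**What to change.** Replace the sentence in SAP 6.4 that rules out subgroup display with wording to this effect: pooled laboratory summaries, changes from baseline, treatment-emergent abnormalities and urinalysis shift tables will be presented by age at enrolment (<12 vs ≥12 years), in line with Protocol 9.4.2, with a combined column in addition. Study 19764's tables need no change.

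If the sponsor prefers to keep the combined display alone, SAP section 7 should record the departure from Protocol 9.4.2 and give the reason. That would make the departure transparent but would not restore the promised tables.

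The cost is SAP wording and more table pages. The age variable is already needed for the adverse-event tables, and no new data are required. One limit remains: only study 19764 is stated to be adult, and the approved indication starts at 12 years, so the ≥12 column may still combine adolescents with adults.

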### **Vital signs**

Summary statistics including changes from baseline will be presented for vital signs (systolic blood pressure, diastolic blood pressure, heart rate, temperature) by visit for study 19764.

Vital signs will not be stratified by subgroups.

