**Table 1-1 Study Schedule of Activities (SoA)**

Procedures	Screening a	Baseline Pre-dose	ED 10-15	ED 50-75 Every 6 months			End of study 100 ED / Early Termination
	Visit 1 2-8 Wks before baseline	Visit 2 Day 1	Visit 3 Wk 8-10 b	Visit 4 Month 6 (±14 days) c	Visit 5 Month 12 (±14 days) c	Visit 6 Month 18 if needed (±14 days) c	Last Visit (+14 days)
Recovery (pre and 15-30 min post injection FVIII levels) h		X	X				X
FVIII level after 48 or 72 hours after last injection				X	X		
In-hospital injection of Jivi		X	X				X
AE review	X	X	X	X	X	X	X
Return used and unused study intervention			X	X	X	X	X
Dispense study intervention for home injections			←==continuously in accordance with IxRS drug dispensing schedule==→				
Injection of Jivi			←=====continuously in accordance with assigned treatment regimen=====→				
Concomitant medication review	X		←=====continuously=====continuously=====→				
Patient diary (EPD) documentation	X		←=====continuously=====continuously=====→				
Interaction between participants and investigators			←=====Monthly contact=====→				

Abbreviations: ADA=anti-drug antibody, AE=adverse event, ALT=alanine aminotransferase, AST=aspartate aminotransferase, ED=exposure days, EPD=electronic patient diary, HIV=human immunodeficiency virus, hrs=hours, IxRS=Interactive voice/web response system, max=maximum, and Wk=week.

- The time interval between Screening and Baseline visit is 2 to 8 weeks.
- Although the allowable visit window is ±14 days, visits must occur within the specified ED range.
- Visits should be scheduled within the visit window so that at least one visit occurs in the 50 – 75 ED range.
- HIV screening will be performed only in case that negative result in patient documentation is older than 1 year at date of screening.
- Only in case of Early Termination Visit before V6.
- In case of any injection related AE, vital signs will be collected in addition post-injection for participants.
- At Baseline, Visit 3 and End of Study/Early Termination Visit, blood samples for immunogenicity will be collected before the in-hospital injection of Jivi.
- Recovery should be measured at least 72 h after last injection of FVIII of Jivi.

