**6.2 Preparation/Handling/Storage/Accountability**

Instructions for the preparation of study interventions can be found in the leaflet for using Jivi.

All study interventions will be stored at the investigational site in accordance with Good Clinical Practice (GCP) and Good Manufacturing Practice (GMP) requirements and the instructions given by the clinical supplies department of the sponsor or its affiliates.

Special storage conditions and a complete record of batch numbers and expiry dates can be found in the sponsor's study file; the site-relevant elements of this information will be available in the investigator site file. On the day of receipt, the responsible site personnel will confirm receipt of study intervention via IxRS.

1. The investigator or designee must confirm appropriate temperature conditions have been maintained during transit for all study intervention received and any discrepancies are reported and resolved before use of the study intervention.
2. Only participants enrolled in the study will receive study intervention and only authorized site staff will supply or administer study intervention. All study intervention must be stored in a secure, environmentally controlled, and monitored (manual or automated) area in accordance with the labeled storage conditions with access limited to the investigator and authorized site staff.
3. The investigator, or the head of the institution (where applicable) is responsible for study intervention accountability, reconciliation, and record maintenance (i.e., receipt, reconciliation, and final disposition records).
4. Further guidance and information for the final disposition of unused study interventions are provided in a separate document.

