### **8.2.3 Vital Signs**

- Vital signs will be measured at Screening, Baseline, and End of Study/Early Termination Visit. In case of any in-hospital injection related AE, vital signs will be measured post-injection for participants.
- Heart rate, respiratory rate, and systolic and diastolic blood pressure will be assessed.
- Blood pressure and heart rate measurements should be preceded by at least 5 minutes of rest for the participant in a supine or seated position without distractions (e.g., television, cell phones).

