#### **10.4.7 Last Visit – ED 100 (End of Study/Early Termination + 14 days)**

This visit should take place at least 72 hours after the previous injection of Jivi.

The following procedures and assessments will be performed in participants reach ED 100 or at the time of premature termination:

- Concomitant medication review
- AE review
- Full physical examination including neurological standard assessment, height, and weight
- Vital signs (Heart rate, respiratory rate, and blood pressure; see Section 8.2.3)
- Urine sample (routine urinalysis and renal biomarkers; see [Table 10-1](#))
- Laboratory evaluation (hematology and clinical chemistry)
- PEG level in plasma
- Blood sample collection **before** administration of study intervention
  - Immunogenicity testing

- Incremental recovery of Jivi
- In-hospital injection of Jivi
- Procedures and blood sample collection **after** administration of study intervention
  - Incremental recovery of Jivi (15-30 min after end of injection; see Section [8.1.2](#))
  - In case of any injection related AE at site, vital signs will be measured
- Return used and unused study intervention
- Check of EPD entries and bleeding history and return EPD
- Return activity tracker in case of early termination before Visit 5

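### The SAP's vital-sign summary includes temperature, which the protocol does not schedule, and omits respiratory rate, which it does

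*SAP*

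**What the plan says.** The SAP (section 6.4, vital signs) plans summary statistics with changes from baseline, by visit and for study 19764 only. It names the parameters in brackets: "systolic blood pressure, diastolic blood pressure, heart rate, temperature".

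The protocol defines the measurements in section 8.2.3: "Heart rate, respiratory rate, and systolic and diastolic blood pressure will be assessed". The same section sets the schedule: "Vital signs will be measured at Screening, Baseline, and End of Study/Early Termination Visit". The visit descriptions for those three visits (sections 10.4.1, 10.4.2 and 10.4.7) repeat the content, for example at the Last Visit: "Vital signs (Heart rate, respiratory rate, and blood pressure; see Section 8.2.3".

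Protocol section 9.4.2 makes two commitments on output. One is a summary: "Laboratory values and vital signs will be summarized". The other is a listing: "Laboratory findings, adverse events, concomitant medications, vital signs, and medical history data will be provided in subject listings". Neither excludes any vital sign.

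**The concern.** The list of parameters to be summarised should be the list of parameters collected, or the SAP should give a reason for the difference. Here the two lists differ and no reason is given. A programmer working from the SAP would build an output for a measurement that the protocol does not request, and would build none for a measurement that it does request.

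What is at stake is whether one safety output is complete and agrees with the protocol. Safety is the primary objective of the study. A reader of the study report who knows section 9.4.2 would expect to find respiratory rate summarised beside heart rate and blood pressure.

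**Working it through.** No sample size, rate or other figure is involved, so the check is a comparison of two lists.

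| Parameter | Collected (protocol 8.2.3 and the three visit descriptions) | Summarised (SAP 6.4) |
|---|---|---|
| Systolic blood pressure | yes | yes |
| Diastolic blood pressure | yes | yes |
| Heart rate | yes | yes |
| Respiratory rate | yes | no |
| Temperature | no | yes |

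Three parameters are on both lists, one is on the protocol list only, and one is on the SAP list only. So 1 of the 4 collected parameters has no planned summary, and 1 of the 4 planned summaries has no protocol-specified collection.

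Possible explanations, each checked against the documents:

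1. *Temperature is collected elsewhere in the protocol.* It is not listed in the schedule of activities, in the physical examination (section 8.2.2) or in any visit description. The word occurs only in section 6.2, for drug shipment: "The investigator or designee must confirm appropriate temperature conditions have been maintained during transit".
2. *Temperature comes from the pooled studies.* SAP 6.4 limits the vital-sign summary to study 19764, so data from 13024 or 15912 cannot account for it.
3. *The SAP follows a different protocol version.* SAP section 7 says that it rests on protocol Version 2.0 of 04 FEB 2020, which is the version reviewed here. The protocol's amendment table mentions no change to the vital-sign parameters.
4. *The change was deliberate.* The SAP's change table (section 7) does not mention vital signs. Its nearest entry concerns descriptions of data rules brought into line with standard macros.
5. *The list is only illustrative.* It carries no such marker, whereas SAP section 6.1 does mark its list of concomitant diseases as examples.
6. *Text is missing.* Neither passage shows a redaction or a gap.

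Extent: there are three scheduled time points (Screening, Baseline, End of Study or Early Termination) in approximately 25-30 participants. SAP section 4.1 takes the last measurement before first treatment as baseline. The change from baseline therefore has one scheduled post-baseline point. It exists only for participants who attend a last visit, and after early discontinuation that visit is held only if possible (protocol section 7.2).

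**The case against.** The strongest case on the other side accepts that the lists differ and disputes that it matters. Most of this stands as a limit on the consequences.

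- *Respiratory rate is not lost.* Section 9.4.2 commits vital signs to subject listings. With 25-30 participants and few time points, each value can be read there. This stands: only the summary statistics and changes from baseline are missing.
- *Temperature may have been recorded.* The CRF is not among the documents, and SAP version 2 (14 MAR 2022) is about two years later than the protocol amendment. A reader might infer that the temperature summary will be empty. The documents show only that the protocol does not specify the measurement.
- *A link to hypersensitivity is not documented.* A reader might infer that leaving out respiratory rate weakens the assessment of hypersensitivity, which is an event of special interest, because extra measurements follow an injection-related event: "In case of any injection related AE, vital signs will be collected in addition post-injection for participants". That instruction covers any injection-related event and does not name hypersensitivity. Where the protocol sets out the work-up for suspected hypersensitivity or loss of efficacy (sections 8.2.1 and 8.3.7), it names inhibitor and antibody testing, recovery and FVIII levels, and no vital signs. Routine values from Screening, Baseline before the injection and the Last Visit would not show an acute reaction in any case. Events of special interest have their own TEAE table in SAP 6.4.
- *A separate listing of the event-triggered values* with the related adverse event would be a matter of preference. It is not needed to resolve the mismatch.

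None of this explains the difference between the lists or meets the commitment in section 9.4.2 to summarise vital signs.

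**Conclusion.** The mismatch is real and can be confirmed from the two texts alone. SAP 6.4 omits summary statistics and changes from baseline for one of four collected vital signs, and plans them for one that the protocol does not schedule.

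The impact is minor. The study tests no hypothesis and all analyses are descriptive. Vital signs are not an endpoint, and no result on inhibitors or ABR depends on them. The documents do not support reading this as a loss of safety data or as a gap in detecting hypersensitivity.

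The conclusion assumes that the bracketed list in SAP 6.4 is meant to be complete, as its wording indicates, and that the listings promised in protocol 9.4.2 will include respiratory rate. Whether the CRF has a temperature field remains open.

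**What to change.** Align the vital-signs paragraph of SAP 6.4 with protocol section 8.2.3:

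- Add respiratory rate to the parameters summarised by visit with change from baseline.
- Check the CRF for temperature. If it is not collected, remove it from the list. If it is, keep it and state where it is collected.
- Record the change in SAP section 7.

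The cost is a one-line text correction and the matching change to the table shell. No new data are needed and study conduct does not change.
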